4.3.2.2 Pancake Initial Escalation Phase (T1P)

The baked egg tolerant (BET) group will undergo a 4-dose initial escalation with pancakes in hospital on a separate day (T1P) to determine the home starting dose of pancake. This should be performed at soonest possible date after baked egg FC.

Pancake Initial Escalation	Pancake Recipe A – 1 egg in 6 pancakes		If dose tolerated, commence build-up at:
Time Point (min)	Pancake amount	Egg Protein (mg)	
0	~1/32	37.5	NA*

20	1/16	75	Step 1: 37.5mg
40	1/8	150	Step 2: 75mg
60	1/4	300	Step 3: 150mg

Table 4: Dosing protocol for Pancake Initial Escalation

*Those reacting at 37.5mg or 75mg will not begin OIT with pancakes but instead begin with cookies (Table 6 Step 11).

BET subjects will commence pancake initial escalation at 37.5mg with increments every 20-30 minutes to a maximum of 300mg unless symptoms develop. The dose tolerated is one which results in no more than mild transient (not lasting more than 20 minutes) symptoms (e.g. itchy mouth) - transient Grade 1 symptoms based on the CoFAR specific grading symptoms for allergic reactions (Table 8). The home starting dose will be one step below the tolerated dose during initial escalation to minimise risk of allergic reactions at home, particularly as the presence of co-factors may decrease reaction threshold.

4.3.2.3 Pancake Build-Up Phase

Each dose increment for pancake will be performed in the Allergy Unit under medical supervision, to confirm tolerance before the new dose is given at home daily for 4 weeks (minimum 3 weeks). Mild transient symptoms (e.g. itchy mouth) to the dose - transient (not lasting more than 20 minutes) Grade 1 symptoms (Table 8) - might be acceptable. If the updosing is not tolerated (i.e. more than mild transient symptoms), the participant will stay on the previously tolerated dose for another 4 weeks (minimum 3 weeks) before returning for repeat updosing.

Pancake Build-up Phase Protocol	Pancake Recipe A – 1 egg in 6 Pancake Recipe B – 2 eggs in 6			Min. no. of months on this step	Cumulative no. of months (minimum)
STEP	Pancake Recipe	Pancake amount	Egg Protein (mg)		
1	A	1/32	37.5	1	1
2	A	1/16	75	1	2
3	A	1/8	150	1	3
4	A	1/4	300	1	4
5	A	1/2	625	1	5
6	A	1	1250	1	6
7	B	1	2500	4	10

Table 5: Pancake Build-up Phase Protocol

When participants have successfully reached the target maintenance dose (Step 7), they will remain on this maintenance dose for a minimum of 16 weeks (or total OIT duration of 18 months, whichever earlier).

4.3.2.4 Cookie Initial Escalation (T1C) and Build-up Phase

The baked egg reactive (BER) group who tolerate at least 3mg of muffin will undergo initial escalation with cookies under medical supervision in the hospital on a separate day (T1C) to determine the home starting dose of cookie. This should be performed at soonest possible date after baked egg FC. The first dose to be administered during initial escalation will be individualised based on the outcome of the baseline baked egg FC. The NOAEL (No Observed Adverse Event Level) – defined as highest dose triggering none or transient Grade 1 symptoms) will be used for this purpose. Subsequent increments will be administered every 20-30 minutes and the maximum number of doses to be administered during the initial escalation is stipulated in Table 6 below. If a given dose triggers symptoms that causes discomfort to the participant or is deemed significant by the research team, no further doses will be administered on that day. Participants will be observed for at least one hour after dosing (2 hours if participant has previously experienced a delayed reaction). Participants will be instructed to have the last well-tolerated dose at home daily for a minimum of 2 weeks, until the next updosing is performed.

Subsequent updosings will be performed at home by the parents once every 2 weeks. The study team will conduct a phone call 2 weeks after the initial escalation and then monthly phone calls, to check on the progress of home updosing, ensure compliance and review any adverse events. When participants successfully reach the target dose (Step 11), they will remain on this dose for a minimum of 2 weeks before undergoing initial escalation with pancake (T2P). Subjects who react at 37.5mg or 75mg during pancake initial escalation will not continue with pancake OIT but instead resume cookie OIT Step 11 for a minimum of another 4 weeks before re-attempting pancake initial escalation.

Cookie Initial Escalation (IE) and Build-up Phase Protocol						
NOAEL at Baseline BE FC (mg)	STEP	Cookie Recipe	Cookie Amount	Egg Protein (mg)	Max Egg Protein at IE (mg)	Max no. of doses at IE
3	1	C	1	1.25	5	3
-	2	C	2	2.5	-	-
-	3	C	4	5	-	-
10	*3.5	D	0.5	6.25	37.5	3
30	4	D	1	12.5	75	3
-	5	D	3	37.5	-	-
100	6	E	1	75	150	2
300	7	E	2	150	300	2
-	8	E	4	300	-	-
1000	9	F	1	625	1250	2
-	10	F	2	1250	-	-
-	11	F	4	2500	-	-

Table 6: Cookie Initial Escalation and Build-up Phase Protocol

* Step 3.5 is only for initial escalation for subjects with NOAEL of 10mg

Egg Content in Cookie Recipes:

- C: 1ml egg in 100 cookies (1.25mg egg protein per cookie)
- D: 10ml egg in 100 cookies (12.5mg egg protein per cookie)
- E: 1 egg in 100 cookies (75mg egg protein per cookie)
- F: 1 egg in 12 cookies (625mg egg protein per cookie)

4.3.2.5 Home Instructions & Checklist

Prior to discharge post initial escalation (pancake or cookie), each family will be provided with:

- A symptom advice sheet including instructions in the prompt recognition of allergic reactions.
- A food allergy action plan. Subjects and their families will be instructed in the use of adrenaline auto-injectors, antihistamines and salbutamol (if known to be asthmatic). The expiry date of medications will be checked, and a prescription for replacements provided if needed.
- A daily dosing diary and instruction sheet which will include the following:
 - Contact information for the team, which will include a dedicated mobile phone number with 24/7 access to a member of the medical team for urgent queries, and an email address which will be checked daily by the research team from Monday to Friday for non-urgent queries.
 - Information to GP / Children's Emergency in writing that the patient is undergoing OIT and that allergic reactions may occur during administration.
 - Instructions on study dose administration including the dose to give their child and advice to avoid intense physical exercise up to 2 hours before and after the dose intake. Subjects will be asked to log all doses taken at home and any resulting adverse events. In the event of any symptoms, the family needs to contact the study team for advice and record all symptoms, duration, timing in relation to immunotherapy dose and any exacerbating factors (e.g. exercise, excessive tiredness, viral illness)
 - Dietary advice on egg avoidance (See Section 6.4).

All control subjects will receive a food allergy action plan, instructions on use of adrenaline auto-injectors, antihistamines and salbutamol if needed, as well as dietary advice on strict egg avoidance.

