1.2.2 Rationale for Study Design

This is a randomised controlled study exploring the efficacy, safety and feasibility of a novel form of egg OIT using pancakes to induce desensitisation and sustained unresponsiveness in egg allergic patients. The control group receiving current standard care of egg avoidance, will be used to control for the incidence of natural resolution of egg allergy over the study period. Safety of OIT and its impact on quality of life measures will also be compared against the risk of accidental reactions among controls who continue strict egg avoidance. Allocation ratio of 2:1 (active:control) allows for more patients to be given a chance to receive OIT.

This is an open label study as we wish to assess a pragmatic approach to OIT with home preparation of pancakes and cookies using store bought eggs, in which blinding will not be feasible nor practical.

Subjects randomised to the active arm will undergo an open baked egg food challenge (FC) to determine their baseline baked egg tolerance. Baked egg tolerant (BET) patients will directly undergo OIT using pancakes. Baked egg reactive (BER) patients will commence OIT with baked egg (cookies), to first achieve desensitisation to baked egg before transitioning to pancakes. Desensitisation will be assessed by an open cooked egg FC at the end of treatment while SU will be assessed by an open cooked egg FC after stopping OIT for approximately 6 weeks.

Updosings for cookies will be done at home under the guidance of the study team based on the safety profile of other home-based baked egg OIT protocols (7),(8). Updosings for pancakes will be performed in the hospital as this has not been evaluated previously.

Subjects randomised to the control arm will continue strict egg avoidance and undergo an open cooked egg FC between 12 and 18 months.

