4.3 Study Visits and Procedures Overview

There will be 9-10 hospital visits for the BET group, 10-11 hospital visits for the BER group over the entire study duration. There will be 2 hospital visits for the control group.

[figure not shown]

Figure 2: POET Study Timeline

Study Timepoints	TS	T0	T1C		T1P/ T2P		T3	T4
	Screening & Cooked Egg FC	Baked Egg FC	Cookie Initial Escalation	Home Cookie Build-up	Pancake Initial Escalation	Hospital Pancake Build-up	Exit Cooked Egg FC	SU FC
Informed consent	X							
Medical history	X							
Concomitant medications	X	X	X		X	X	X	X
Adverse events		X	X	X	X	X	X	X
Physical exam	X	X	X		X	X	X	X
Spirometry		(X)					(X)	
Asthma control test	X	(X)					(X)	
SCORAD	X							
POEM	X							
Skin Prick Test	X*						X	X
Blood test	X*						X	X
HRQL Assessments	X		X		X		X	X

Table 1: Study Procedures

(X) may be performed, depending on clinical need; X* - Results from SPT/ IgE performed within 3 months prior will be used and need not be repeated

X are procedures applicable to control subjects

FC – Food Challenge; SU – Sustained Unresponsiveness

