9.2.2 Analysis of Secondary Outcomes

The following secondary analyses will be performed:

- Proportion of subjects who tolerate 4443mg or more of egg protein in the active and control groups, following cessation of all egg intake for 6 weeks (sustained unresponsiveness), using a two-sided Fisher's exact test.
- The incidence of adverse events experienced between active and control groups. Statistical differences will be determined using two-sided Fisher's exact test for proportions; non parametric tests for graded reactions. Logistic regression will be used to assess the association of age, gender, asthma status and prior history of anaphylaxis with incidence of adverse events.
- Completion rates in the active and control groups will be compared using a two-sided Fisher's exact test.
- Change in quality of life assessments before and after OIT, as assessed by FAQL-Q in children, teenagers and their parents – between the active and control groups using two independent sample t test (or Mann-Whitney U test if normality assumption is not tenable). The changes within each group will be assessed using paired t test (or Wilcoxon signed rank test if normality assumption is not tenable).
- Immunological outcome measures pre- and post- of OIT, using paired t test (or Wilcoxon signed rank test if normality assumption is not tenable) within each group.

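### The plan requires adverse events to be kept in a diary but supplies one only after initial escalation, and controls have far fewer scheduled contacts, so the between-arm adverse event comparison is likely to under-count control events.

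*Combined protocol and SAP*

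**What the plan says.** **Who is handed a diary.** Section 4.3.2.5 opens with "Prior to discharge post initial escalation (pancake or cookie), each family will be provided with" and then lists the pack, which includes "A daily dosing diary and instruction sheet which will include the following". On its use: "Subjects will be asked to log all doses taken at home and any resulting adverse events". Families are also told to contact the team about any symptoms and to note their timing and possible cofactors. Initial escalation, with pancake or cookie, takes place only in the active arm.

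**What controls are handed.** The same section ends with their list: "All control subjects will receive a food allergy action plan, instructions on use of adrenaline auto-injectors, antihistamines and salbutamol if needed", together with dietary advice. It names no diary and no symptom sheet.

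**General recording rules.** Section 7.3 has all adverse events entered in the subject's diary from consent, until resolution or 30 days after study treatment is completed. Section 6.6 has participants or parents note medication, rescue medication included, on home diary cards. Neither rule is restricted by arm.

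**Scheduled contact.** Section 4.3: "There will be 2 hospital visits for the control group". It gives 9-10 visits for the baked egg tolerant (BET) group and 10-11 for the baked egg reactive (BER) group. Section 4.3.2.6 puts the control challenge (T3) between 12 and 18 months. The only scheduled calls that review adverse events are in the cookie phase (4.3.2.4).

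**Use of the data.** Section 9.2.2 lists as a secondary analysis "The incidence of adverse events experienced between active and control groups", tested by a two-sided Fisher's exact test, with non-parametric tests for graded reactions. Section 1.2.2 explains the purpose: the safety of OIT "will also be compared against the risk of accidental reactions among controls who continue strict egg avoidance".

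**The concern.** A comparison of event incidence is fair only if an event of a given kind is about equally likely to be recorded in either arm. Here the recording rule covers everyone, but the step that puts a diary in the family's hands covers only the active arm, and the occasions on which staff would ask about events differ several-fold. The trial is open label, so equal ascertainment has to be built into the procedures.

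The events most exposed are mild accidental reactions at home, which are easily forgotten by a visit a year or more later. These are also the events that 1.2.2 names as the comparator. If they are under-counted in controls, avoidance looks safer than it is and OIT looks relatively worse, for a reason unrelated to OIT. Analysis cannot recover events that were never recorded.

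**Working it through.** **1. Reproducing the visit counts.**
- Control: TS + T3 = 2, as stated in 4.3.
- BET: TS, T0, T1P, T3 and T4 make 5. Hospital updosings to Step 7 number 4, 5 or 6 when home dosing starts at Step 3, 2 or 1 (Tables 4 and 5). Total 9 to 11, against 9-10 stated.
- BER: one more visit (T1C), so 10 to 12, against 10-11 stated.

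The control figure matches exactly. The active ranges match at the lower end, and the upper end is one higher if a child starts at Step 1. On the stated figures the ratio of scheduled visits is 9/2 = 4.5 to 11/2 = 5.5.

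**2. Recording routes side by side.**

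| | Active | Control |
|---|---|---|
| Rule to record in a diary (7.3, 6.6) | Yes | Yes |
| Stated step that supplies a diary (4.3.2.5) | After initial escalation | None |
| Scheduled hospital visits (4.3) | 9-11 | 2 |
| Scheduled adverse event calls (4.3.2.4) | Cookie phase: at 2 weeks, then monthly | None stated |
| End of recording window (7.3) | 30 days after study treatment | Not defined, as there is no study treatment |

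Active children between consent and initial escalation also have no stated diary.

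**3. What unequal capture could do (illustration).** The arm sizes, 22 and 11, are from 3.1. The documents give no event or capture rates, so the rest is assumed: true proportion with at least one event *r*, the same in both arms; active capture 0.95; control capture 0.95*k*.

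Expected observed gap = 0.95*r* − 0.95*kr* = 0.95*r*(1 − *k*).

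With *k* = 0.5:
- *r* = 0.3: 0.285 − 0.1425 = 0.1425, or 14 points
- *r* = 0.5: 0.475 − 0.2375 = 0.2375, or 24 points
- *r* = 0.7: 0.665 − 0.3325 = 0.3325, or 33 points

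The chance of two-sided Fisher p<0.05 is the sum of Bin(x; 22, 0.95*r*) × Bin(y; 11, 0.95*kr*) over all tables (x, y) that the test rejects:

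| True risk | Equal capture | *k* = 0.5 |
|---|---|---|
| 30% | 3% | 6% |
| 50% | 3% | 19% |
| 70% | 3% | 33% |

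Varying *k* from 0.75 to 0.25 moves the gap from 0.95 × 0.3 × 0.25 = 7 points to 0.95 × 0.7 × 0.75 = 50 points.

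**4. If the true risks differ.** Let the true risks be *a* (active) and *c* (control). The observed gap is 0.95*a* − 0.95*kc*; under equal capture it would be 0.95*a* − 0.95*c*. The excess is 0.95*c*(1 − *k*), which does not involve *a*. The point gaps in step 3 therefore also measure the inflation of a real gap, with *r* read as the control risk. The rejection rates do not carry over.

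**The case against.** **Controls may well have a diary.** The item in 4.3.2.5 is a dosing diary, which a child without doses does not need, and 7.3 and 6.6 apply to everyone. This stands. A reader might infer that the plan denies controls a diary, but the documents support only that it requires one and does not say how or when controls receive it.

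**Control events need not rest on recall alone.** Controls attend T3, where they can be questioned, 7.3 provides for questioning, and 7.5 has safety monitored from enrolment to completion. A reader might also infer that Table 1 omits adverse event collection for controls. That cannot be judged: its footnote refers to marks for control procedures that cannot be told apart in the text available. Even so, one questioning visit at 12 to 18 months is not equivalent to the active schedule.

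**Active follow-up is not uniformly close.** Roughly 4-weekly visits apply only to pancake build-up. No interim visit or call is scheduled during the minimum 16-week maintenance period, and the logging instruction centres on doses. The assumed 95% active capture may be generous for accidental reactions.

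**Equal true risk is unrealistic here.** Section 2.4.1 expects more reactions under OIT than under avoidance, and dose reactions can occur only in the active arm. The realistic error is therefore an inflated real gap rather than a false positive. This stands, and it limits what the rejection rates mean.

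**Part of the visit difference is inherent to OIT.** True, but a diary and a phone call can be made the same in both arms.

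**Conclusion.** The point holds as an inconsistency between 4.3.2.5 and sections 7.3 and 6.6, together with clearly unequal scheduled contact: 2 control visits against 9-11, plus calls in the cookie phase. The inequality of contact remains whatever is decided about the diary. The likely direction is under-counting in controls and a gap inflated against OIT, mainly for accidental and other non-dose reactions.

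The size is unknown. The 14, 24 and 33 points, and the 7 to 50 point range, depend on assumed capture rates and show sensitivity; they are not estimates for this trial. The 6%, 19% and 33% rejection rates depend further on equal true risk.

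The matter touches a secondary safety comparison. The challenge-based primary outcome is unaffected. The change should be made, because it is cheap and lost events cannot be restored later.

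**What to change.** - **4.3.2.5, reconciled with 7.3 and 6.6:** give every participant, controls included, the same event and rescue-medication diary at randomisation. Active families keep the dosing log in addition.
- **Contact:** add a short adverse event call on the same fixed schedule, with the same questions, in both arms.
- **7.3:** state the adverse event window for controls, since its end is now tied to study treatment.
- **9.2.2:** keep the overall comparison. Also report reactions to study doses separately (active arm only, descriptive) from all other reactions (compared between arms).

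**Cost:** diaries for about 11 control families, and brief periodic calls to up to 33 families by the existing team. Controls would have slightly more contact than under usual care.

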The BER group who tolerate at least 3mg of muffin in the baseline baked egg FC will undergo initial escalation with cookies in hospital (T1C). The first dose to be administered during the initial escalation will be individualised based on the outcomes of the baseline baked egg FC while the home starting dose will be the last dose tolerated during initial escalation. The starting cookie dose will be administered daily at home for a minimum of 2 weeks. Subsequent updosings will be done at home on a 2-weekly basis. When participants have successfully reached the target dose (Table 6 Step 11), they will remain on this dose for a minimum of 2 weeks before undergoing pancake initial escalation to begin pancake OIT (T2P). Those reacting at 37.5mg or 75mg will not begin OIT with pancakes but instead resume cookie OIT Step 11 for another minimum 4 weeks before re-attempting pancake initial escalation.

All participants who have completed at least 16 weeks of maintenance pancake OIT will undergo an open cooked egg FC at the end of treatment to assess for desensitisation (T3). Participants who tolerate 4443mg of cooked egg and deemed successfully desensitised will then stop OIT for approximately 6-8 weeks prior to returning for a repeat cooked egg FC to assess for sustained unresponsiveness (T4).

Participants who tolerate 4443mg of cooked egg at SU FC will be allowed ad libitum cooked egg consumption post study. Participants who develop allergic reactions at SU FC will resume previous maintenance dose.

Control subjects will receive the current best standard care, i.e. strict egg avoidance with provision of rescue medication and training. They will then undergo an open cooked egg FC between 12 and 18 months to assess for cooked egg tolerance.

Approximate time to complete study recruitment is 12 months. Total OIT duration from initial escalation to desensitisation FC is a minimum of 12 months and maximum of 18 months.

[figure not shown]

Figure 1: POET Study Design

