6.4 Specific Restrictions / Requirements

Subjects in the control arm will be advised strict egg avoidance including all baked egg products. However for those who were already previously tolerating baked egg products, they will be allowed to continue consumption of baked egg products outside of study, up to a maximum of 2.5g baked egg protein (approximately equivalent to a slice of cake or one muffin) per week.

Subjects in the BER group undergoing cookie OIT will be counselled for strict egg avoidance including all baked egg products outside of the study treatment. Subjects in the BET group who had tolerated baked egg products prior to study will be allowed to continue the consumption of baked egg products outside of study, up to a maximum of 2.5g baked egg protein (approximately equivalent to a slice of cake or one muffin) per week. This limit is placed because baked egg consumption in BET subjects may enhance desensitisation to cooked egg, and subjects taking larger quantities of baked egg outside of pancake OIT may have better rates of desensitisation. However, as pancake OIT outcomes should be assessed

in a real-world setting, this will include allowing baked egg consumption in egg allergic children who are already tolerating baked egg.

Subjects who are receiving anti-IgE therapy, oral immunosuppressants, beta-blocker, ACE inhibitor or immunotherapy for other allergens will fall under the study's exclusion criteria and be withdrawn from study.

Subjects will be advised to avoid intense physical exercise up to 2 hours before and after each OIT dose intake.

6.5 **Blinding**

This is an open label study. Blinding will not be performed.

6.6 **Concomitant therapy**

Participants may continue usual medications, including those taken for asthma, rhinitis, and eczema during the study. Antihistamines must not be taken on the day of updosing and must be stopped prior to FC visits as per Section 4.3.2.8. Participants (or their parents) will be asked to document any use of medication (including rescue medication) in home diary cards.

All medications (prescription and over the counter) taken by the participant should be documented.

7 **SAFETY MEASUREMENTS**

7.1 **Definitions**

An adverse event (AE) is any untoward medical occurrence in a patient or clinical investigation subject administered a pharmaceutical product and which does not necessarily have a causal relationship with this treatment.

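### The control diet is stated inconsistently: strict egg avoidance in 1.2.2, 4 and 4.3.2.5, but capped baked egg allowed in 6.4, and on-study baked egg intake is not recorded in either arm

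*Combined protocol and SAP*

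**What the plan says.** Three places give the control diet without qualification.

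- Section 1.2.2: "Subjects randomised to the control arm will continue strict egg avoidance". The same section says the control group "will be used to control for the incidence of natural resolution of egg allergy over the study period".
- Section 4: "Control subjects will receive the current best standard care, i.e. strict egg avoidance with provision of rescue medication and training".
- Section 4.3.2.5, which sets out what families are told, ends with a sentence for controls: instructions on rescue medication, "as well as dietary advice on strict egg avoidance".

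Section 6.4 opens in the same way, "Subjects in the control arm will be advised strict egg avoidance including all baked egg products", and then makes an exception. For controls who were already tolerating baked egg, "they will be allowed to continue consumption of baked egg products outside of study, up to a maximum of 2.5g baked egg protein" per week. Active BET children who ate baked egg before the study get the same permission and cap. Active baked egg reactive (BER) children are to avoid it outside study treatment. The stated reason for the cap is that "baked egg consumption in BET subjects may enhance desensitisation to cooked egg"; the stated reason for allowing baked egg at all is a real-world setting.

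The active families' list in 4.3.2.5 carries a cross-reference, "Dietary advice on egg avoidance (See Section 6.4"). The control sentence below it carries none.

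**The concern.** Children who eat baked egg are eligible: the exclusion in 3.4 covers current consumption of egg products other than extensively heated egg in baked foods. The conflict therefore concerns children who can be enrolled in either arm.

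The exposure also bears on the primary outcome. Section 6.4 says it may enhance desensitisation to cooked egg, and 1.1 mentions some suggestion that it may speed resolution. If control families are advised from 4.3.2.5 and active families from 6.4, the arms differ in something besides pancake oral immunotherapy (OIT). If both are advised from 6.4, the arms are treated alike on this point, but the control arm is not the one that 1.2.2 describes as showing natural resolution under avoidance. Without a record of intake, a reader of the results could not tell how far either situation applied.

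**Working it through.** This is mainly a comparison of text. The plan gives no figure for the effect of baked egg, so there is none to reproduce on the point itself.

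**1. Can the statements be read together?** Sections 1.2.2, 4 and 4.3.2.5 could be shorthand for 6.4. Against that, 6.4's own first sentence on controls uses strict avoidance to include baked egg, and the control sentence in 4.3.2.5 neither mentions the exception nor points to it. A staff member working from 4.3.2.5 has no prompt to apply it.

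**2. What follows from each reading, for a child eating baked egg at entry?**

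| Text followed | Control | Active, BET | Active, BER |
|---|---|---|---|
| 4.3.2.5 as written | told to stop | may continue, capped (via 6.4) | told to avoid |
| 6.4 | may continue, capped | may continue, capped | told to avoid |

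The first row would tend to favour the active arm. The second row contains a smaller asymmetry. Control permission rests on reported prior tolerance, because only the active arm has the baked egg challenge (4.3.2.1). A child who had eaten some baked egg but fails that challenge is BER and must avoid it in the active arm, yet could continue as a control. That would tend to narrow the difference. The net direction is not fixed.

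**3. Is intake recorded or balanced?** Table 1 has no diet item. The diary in 4.3.2.5 logs OIT doses and adverse events, and 6.6 adds medication. The minimisation factors in 4.1 are age, egg-specific IgE and asthma on inhaled corticosteroids. Section 9.2 has no analysis by baked egg intake.

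**4. Scale.**

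- One control: 1/11 = 9.1 percentage points. One active child: 1/22 = 4.5 points.
- Section 1.1 puts baked egg tolerance at about 70%, and 0.70 × 11 = 7.7, so about 8 of 11 controls might be tolerant. This is a ceiling on those affected, because not every tolerant child eats baked egg.
- Assuming independent binomials at 70% with 22 and 11 children, the chance that the arms differ by 20 points or more in the tolerant share is about 23%.

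**5. Sensitivity to the control rate.** The plan's total of 33 reproduces with an unpooled normal approximation: control n = (0.15 × 0.85 + 0.65 × 0.35/2) × (1.960 + 0.842)² / 0.50² = 7.57; total 3 × 7.57 = 22.7; 22.7/0.7 = 32.5, so 33. Exact power of the planned two-sided Fisher test, with the active rate held at 65%:

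| Assumed control rate | 22 v 11 | 16 v 8 |
|---|---|---|
| 15% (plan) | 75% | 59% |
| 20% | 62% | 48% |
| 25% | 49% | 38% |
| 30% | 37% | 29% |

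Rates above 15% are assumptions. The table shows how sensitive the trial is to its control rate, whatever the cause. It does not estimate a baked egg effect.

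**The case against.** The strongest reply is that 6.4 is the dedicated section on restrictions and gives a complete control rule: avoidance, a named exception and a cap, with the same cap for active BET children. Allowing baked egg is deliberate, its possible effect is acknowledged, and a pragmatic rationale is given. The other sections are summaries. This is also a single-site trial, so different sites cannot apply different rules.

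Much of this stands. A reader might infer that the comparator is undefined; it is not, because 6.4 defines one. A reader might infer that the design gives the arms different baked egg exposure; under 6.4 baked-egg eaters among controls and BET children have the same allowance. A difference by arm is a risk created by the conflicting wording, and by the challenge being done in one arm only.

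It might also be inferred that nobody could establish afterwards who ate baked egg. That goes too far. Eligibility turns on which egg products a child currently eats, medical history is taken at TS, and eligibility source documents are retained, so entry status is probably recoverable. On-study intake and adherence to the cap are what go unrecorded.

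The reply does not remove the conflict between 4.3.2.5 and 6.4, nor explain why only the active list carries the cross-reference.

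**Conclusion.** The point holds as an inconsistency with a credible route to bias. Three sections give controls avoidance without exception and a fourth permits capped baked egg. The section closest to what families are told is worded so that, if followed literally, a co-exposure the protocol links to the primary outcome would be withdrawn from controls only.

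It is tempting to go further and say that the OIT effect would be inflated, or the control rate lifted above 15%, by some number of points. The documents do not support that. They say only that baked egg may help. The 70% is tolerance, not consumption. Section 1.1 also says baked egg tolerant children appear to outgrow egg allergy earlier, so a better outcome in eaters would mix prognosis with exposure. Nor do the documents say whether the cohorts behind the 15% included baked-egg eaters.

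The conclusion rests on the text as it stands and assumes that no separate family instruction sheet resolves the matter. The sample size does not change.

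**What to change.** Reconcile 1.2.2, 4 and 4.3.2.5 with 6.4. The control sentence in 4.3.2.5 should point to whichever rule the sponsor keeps, as the active list already does, and the comparator should be described accordingly wherever it is named. Which dietary rule applies is for the sponsor. A single wording for every child in both arms is not being asked for, since 6.4 treats BER children separately.

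Record baked egg intake (yes or no, and approximate weekly amount) at TS and T3 in both arms, and report it descriptively by arm. With 11 controls, no formal subgroup analysis is warranted.

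The cost is wording changes and two diet questions at visits that both arms already attend. Recall at T3 over 12 to 18 months will be imprecise, but it would still show whether the arms differed grossly and whether the cap was broadly kept.
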